12.1 Populations

12.1.1 Efficacy Analysis

The FAS population will serve as the primary population for the analysis of tumor response and other efficacy-related data. Subjects will be excluded for FAS for the following reasons:

- No baseline data
- Failure to receive at least one dose of tipifarnib
- No post-baseline endpoint data subsequent to at least 1 dose of study drug

Subjects will be grouped in the FAS population according to cohort and tumor histology. A supportive analysis using the Per-Protocol population will be performed for the tumor response analysis. The Per-Protocol population excludes subjects due to important deviations from the protocol that may substantially affect the results of the primary analysis, such as not taking at least 80% of the intended dose in cycle 1. The final determination on protocol violations, and thereby the composition of the Per-Protocol population, will be made prior to locking the clinical database and final analysis and will be documented in a separate memorandum.

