12.2 Endpoints

12.2.1 Efficacy

The objective response rate will be estimated for each tumor histology type evaluated. The estimate of the objective response rate will be calculated based on the maximum likelihood estimator (i.e., crude proportion of subjects whose best overall response is Complete Response (CR) or PR. The estimate of the objective response rate will be accompanied by 2-sided 95% exact binomial confidence intervals.

The duration of objective response will be calculated for subjects who achieve CR or PR. For such subjects, the duration of objective response is defined as the number of days from the start date of PR or CR (whichever response is achieved first) to the first date that progressive disease is objectively documented. Disease progression will be determined by the Investigator using RECIST (version 1.1). The duration of objective response will be right-censored for subjects who achieve CR or PR and meet 1 of the following conditions: 1) non-protocol anticancer treatment started before documentation of disease progression, 2) death or documented disease progression after more than 1 missed disease assessment visit, or 3) alive and does not have documentation of disease progression before a data analysis cutoff date.

The duration of objective response will be summarized descriptively using the Kaplan-Meier method. The 50th percentile of the Kaplan-Meier distribution will be used to estimate the median response duration.

Progression free survival will be defined as the time (in months) from enrollment to either first observation of progressive disease or occurrence of death due to any cause within 126 days (approximately 2 time intervals for tumor assessments) of either first administration of tipifarnib or the last tumor assessment. In subjects without a progression date or with a death date more than 126 days after the first administration of study drugs or the last tumor assessment, the PFS time should be censored on the date of last tumor assessment or date of first administration of study tipifarnib. Progression free survival analyses should consider tumor assessments after treatment discontinuation or metastatic surgery. Sensitivity analyses for PFS will be performed according to the FDA Guidance for Industry Clinical Trial Endpoints for the Approval of Cancer Drugs and Biologics (May 2007).

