6. ANALYSIS POPULATIONS

Enrolled subjects are those that signed informed consent and either met all inclusion and exclusion criteria or were authorized by Sponsor to receive study drug treatment.

Full analysis set (FAS)

The FAS population will serve as the primary population for the analysis of tumor response and other efficacy-related data. Subjects will be excluded from FAS for the following reasons:

- No baseline data
- Failure to receive at least one dose of tipifarnib
- No evaluable post-baseline endpoint data subsequent to at least 1 dose of study drug
- If the only post-baseline assessment is Stable Disease and it occurred prior to 6 weeks from first dose.

Protocol KO-TIP-001

Subjects will be grouped in the FAS population according to cohort as described in Section 4.1.

Per-Protocol (PP) Population

A supportive analysis using the PP population will be performed for the tumor response analysis. The PP population excludes subjects due to major deviations from the protocol that may substantially affect the results of the primary analysis. The final determination on protocol violations, and thereby the composition of the PP population, will be made prior to locking the clinical database and final analysis and will be documented in a separate memorandum.

All Subjects as Treated (ASaT) population

The ASaT population will be used for the analysis of safety data. The ASaT population consists of all enrolled subjects who receive at least one dose of tipifarnib. At least one laboratory or vital sign measurement obtained subsequent to at least one dose of study drug is required for inclusion in the analysis of a specific safety parameter. To assess change from baseline, a baseline measurement is also required.

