9.1. Primary Efficacy Analyses

The objective response rate (ORR) of tipifarnib in subjects with locally advanced unresectable or metastatic, relapsed and/or refractory, HRAS mutant non hematological malignancies will be estimated. The primary endpoint will be response assessments according to RECIST 1.1

The estimate of the objective response rate will be calculated based on the maximum likelihood estimator (i.e., crude proportion of subjects whose best overall response is Complete Response (CR) or Partial Response (PR)). The estimate of the objective response rate will be accompanied by 2-sided 95% Confidence Interval (CI). When $N\hat{p} > 5$, where N is number of subjects, the 95% CI can be estimated using the Wilson, score test based, method.

Protocol KO-TIP-001

A summary of the ORR will be presented for the FAS population. A corresponding summary for the PP population will be presented as a sensitivity analysis. In addition, the data will be presented for the subgroups as described in Section 7.5.

Data on tumor assessment information, target tumor assessment, non-target tumor assessment, new lesion assessment and overall response assessment will be displayed in listings.

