9.2. Exploratory Efficacy Analyses

The duration of objective response (DOR) will be calculated for subjects who achieve CR or PR. For such subjects, the DOR is defined as the number of days from the start date of PR or CR (whichever response is achieved first) to the first date that progressive disease is objectively documented. Disease progression will be determined by the Investigator using RECIST (version 1.1). The DOR will be right-censored at the date for subjects who achieve CR or PR and meet 1 of the following conditions: 1) when non-protocol anticancer treatment started before documentation of disease progression, 2) when death prior to documented disease progression or documented disease progression after more than 1 missed disease assessment visit, or 3) when alive and does not have documentation of disease progression before a data analysis cutoff date. (Therefore, analysis cutoff date will be used as the censoring date).

Progression free survival (PFS) will be defined as the time (in months) from first dose (Cycle 1 Day 1) to either first observation of progressive disease or occurrence of death due to any cause within 126 days (approximately 2 time intervals for tumor assessments) of either first administration of tipifarnib or the last tumor assessment. Observation of progressive disease can be by either documented radiographic progression (i.e., scan results) or documentation of symptomatic or clinical progression agreed upon and documented by investigators. In subjects without a progression date or with a death date more than 126 days after the first administration of study drugs or the last tumor assessment, the PFS time should be censored on the date of last tumor assessment or date of first administration of study tipifarnib. PFS analyses should consider tumor assessments after treatment discontinuation or metastatic surgery.

The DOR and PFS, will be summarized descriptively using the Kaplan-Meier (KM) method. The 25th, 50th, and 75th percentiles of the Kaplan-Meier distribution will be used to describe the median response duration and median PFS.

The median DOR and PFS and corresponding pointwise 95% confidence interval will be displayed by cohort for the FAS population and for the PP population, and for the subgroups.

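### The primary ORR set leaves out treated subjects who cannot be responders, and no all-treated ORR with a confidence interval is planned beside it

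*SAP*

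**What the plan says.** SAP section 6 names the FAS as the primary population for tumour response and other efficacy data. Two of its exclusions apply to subjects who have been dosed and have a baseline: "No evaluable post-baseline endpoint data subsequent to at least 1 dose of study drug" and "If the only post-baseline assessment is Stable Disease and it occurred prior to 6 weeks from first dose".

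Protocol section 12.1.1 also makes the FAS primary, but its matching rule reads "No post-baseline endpoint data subsequent to at least 1 dose of study drug". It has neither the word *evaluable* nor the early stable disease rule. SAP section 14, which lists changes from the protocol, mentions neither difference.

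Protocol section 8.2 allows dosed subjects without post-baseline endpoint data to be replaced. SAP section 7.6 handles missing data by reducing the denominator.

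SAP section 9.1 plans ORR on the FAS and adds: "A corresponding summary for the PP population will be presented as a sensitivity analysis". It also plans ORR for the section 7.5 subgroups. The set of all dosed subjects (ASaT) has another purpose: "The ASaT population will be used for the analysis of safety data".

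On the interval, the protocol specifies "2-sided 95% exact binomial confidence intervals". SAP section 9.1 says that, when N times the observed proportion exceeds 5, "the 95% CI can be estimated using the Wilson, score test based, method".

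**The concern.** ORR is the primary endpoint of a single-arm trial, so the choice of denominator feeds straight into the headline result. Confirmation of response is required (Protocol section 10.1, SAP section 4.1). A dosed subject without evaluable post-baseline data, or with only an early stable disease reading, cannot be a confirmed responder. Removing such subjects therefore raises the ORR, or leaves it at zero if there are no responders.

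The planned sensitivity analysis does not show this effect. The per-protocol set is defined by removing subjects with major deviations, and does not put these subjects back.

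The term *endpoint data* is also undefined. SAP section 9.2 counts as PFS events a death within 126 days of first administration and "documentation of symptomatic or clinical progression agreed upon and documented by investigators". A subject with either event before any scan could be read as having endpoint data, and stay in the ORR denominator as a non-responder, or as having none, and leave it. The same data could then give two primary ORRs.

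**Working it through.** **1. The plan's own design figures.** Inputs from SAP section 5: 11 subjects in stage 1, stop at one or fewer responses, 7 more in stage 2, success at 4 or more of 18, null 10%, alternative 30%. The probability of success is the sum over x = 2 to 11 of P(Bin(11,p) = x) × P(Bin(7,p) ≥ 4 − x).

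| Quantity | Stated | Recomputed |
|---|---|---|
| One-sided alpha (p = 10%) | 0.087 | 0.08749 |
| Power (p = 30%) | 80% | 0.8001 |
| Stop at stage 1, p = 10% | 0.697 | 0.6974 |
| Stop at stage 1, p = 30% | 0.113 | 0.1130 |

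All reproduce, for evaluable subjects.

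**2. The factor.** With N treated subjects, x responders and a share f excluded, none of them a responder:

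- all-treated ORR = x/N
- FAS ORR = x/(N(1−f)) = all-treated ORR × 1/(1−f)

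The documents do not give f. Over an assumed range, an all-treated ORR of 30% reads in the FAS as 30.0% (f = 0), 31.6% (5%), 33.3% (10%) or 37.5% (20%).

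**3. Subject counts at planned sizes.** Responder counts are assumed. The FAS is held at its planned size, which assumes that excluded subjects are replaced. With k excluded at n evaluable, f = k/(n+k).

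| Set | FAS | Excluded | f | All treated | Shift (points) |
|---|---|---|---|---|---|
| Cohort 1 | 4/18 = 22.2% | 1 | 5.3% | 4/19 = 21.1% | 1.2 |
| Cohort 1 | 4/18 = 22.2% | 2 | 10.0% | 4/20 = 20.0% | 2.2 |
| HNSCC | 9/30 = 30.0% | 1 | 3.2% | 9/31 = 29.0% | 1.0 |
| HNSCC | 9/30 = 30.0% | 3 | 9.1% | 9/33 = 27.3% | 2.7 |

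Without replacement, 18 treated with 4 responders is 4/18 = 22.2%. Excluding one or two gives 4/17 = 23.5% or 4/16 = 25.0%, shifts of 1.3 and 2.8 points.

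**4. Effect of the undefined term.** Assume 33 treated HNSCC subjects, 9 responders and 3 with no scan, of whom 2 died or progressed clinically early.

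| Reading | ORR | Exact 95% CI | Wilson 95% CI |
|---|---|---|---|
| FAS, such events are not endpoint data | 9/30 = 30.0% | 14.7–49.4 | 16.7–47.9 |
| FAS, such events are endpoint data | 9/32 = 28.1% | 13.7–46.7 | 15.6–45.4 |
| All treated | 9/33 = 27.3% | 13.3–45.5 | 15.1–44.2 |

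The largest difference is 2.7 points, against an exact interval about 35 points wide (49.4 − 14.7 = 34.7).

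**5. Reach of the early stable disease rule.** The first scheduled scan is Cycle 2 Day 22 ± 5 days (Protocol Table 1, footnote 9). That is study day 28 + 22 = 50 ± 5, or 44 to 54 days after first dose. The rule's limit is 6 × 7 = 42 days. Scheduled scans fall outside it, so only an early unscheduled or end-of-treatment scan can trigger it.

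**6. Interval method.** For 4/18, N times the proportion is 4, so the Wilson condition in SAP section 9.1 is not met and the SAP names no other method. For 9/30 it is 9 and the condition is met.

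**The case against.** The strongest reply is that the FAS is a planned feature. The design counts evaluable subjects throughout, the stage 1 decision is stated on an FAS basis, and Protocol section 8.2 foresees replacement. An ORR in evaluable subjects is what the trial set out to estimate. This stands.

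It also answers a stronger reading. With an all-treated ORR of 10%, f = 10% and 18 evaluable subjects filled by replacement, the chance of four or more responses under the two-stage rule is 0.118. A reader might infer that 0.087 is understated. The documents do not support that, because the decision rule is set in evaluable subjects and 0.087 is right for them.

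The size is unknown and may be zero; nothing in the documents supports an f as high as 20%. This also stands.

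Much of the information is recoverable. SAP section 8.1 gives counts per analysis population, and section 9.2 gives best response with population inclusion per subject. A reader could rebuild the all-treated proportion. That reduces the weight of the point, but it is no substitute for a reported estimate with its interval, and it does not settle the undefined term.

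On that term, the SAP leans towards keeping early deaths in: PFS is analysed on the FAS and counts deaths within 126 days of first administration. Section 6 still does not say so. The word *evaluable* may be only a clarification, since the protocol itself speaks of evaluable subjects.

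Finally, SAP version 4.0 is dated 5 January 2021, after the April and September 2020 data cuts that it names. A reader might infer that the exclusions were written with results in view. The documents do not show when either rule entered the SAP, so that inference is unsupported.

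**Conclusion.** The point holds as a reporting gap, minor to should-fix. The FAS ORR is at least as high as the all-treated ORR, by the exact factor 1/(1−f), and the plan contains no all-treated estimate with a CI. This rests only on the exclusion rules and the requirement for confirmation. The size rests on assumed exclusions: about 1 to 3 percentage points for one to three subjects at the planned evaluable sizes, and nothing if no one is excluded.

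It would go too far to say that the plan materially overstates ORR. The excluded share is not in the documents, and the shift in these examples is small beside the interval. The undefined term is a real ambiguity whatever f turns out to be. The unlisted early stable disease rule is a documentation gap with little expected effect on the numbers.

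**What to change.** 1. **SAP section 9.1:** add a supportive ORR with 95% CI by cohort for all treated subjects. Use the ASaT set less the Amendment 4.2 subject, whom SAP section 5 already leaves out of the primary analysis. Count non-evaluable and early-stable-disease-only subjects as non-responders. Use one stated interval method for this row and the FAS row, for example the exact binomial of Protocol section 12.2.1, which applies at any count. Keep the FAS primary and label the row as added after the 2020 data cuts.
2. **Exclusions:** report by cohort the number left out of the FAS under each rule.
3. **SAP section 6:** state whether death or documented clinical progression before a first scan counts as post-baseline endpoint data, consistently with the PFS events in section 9.2. If this changes FAS membership, disclose that it was settled after the data cuts and show the ORR both ways.
4. **SAP section 14:** list the early stable disease rule, and the word *evaluable* if it changes membership. This part is documentation only.

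The cost is one SAP revision and one extra table row per cohort, with no new data or subjects; SAP section 8.3 already summarises some items on both ASaT and FAS. The downside is that a slightly less favourable ORR may appear beside the FAS figure, and that it is not prespecified relative to the 2020 cuts.

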8.2 Subject Identification and Replacement of Subjects

Each subject will be assigned a unique subject identifier. This unique identifier will be on all eCRF pages. Subjects who do not receive at least one dose of tipifarnib will be replaced. Subjects who do not have post-baseline endpoint data subsequent to at least 1 dose of study drug may be replaced.

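### PFS, and by default OS, is run on a set defined by data after first dose, so some early events that the SAP itself counts can be dropped

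*SAP*

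**What the plan says.** **Population.** SAP 6 states: "The FAS population will serve as the primary population for the analysis of tumor response and other efficacy-related data". Besides subjects with no baseline data and subjects never dosed, the FAS excludes two groups on what happens after the first dose:

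- third exclusion: "No evaluable post-baseline endpoint data subsequent to at least 1 dose of study drug"
- fourth exclusion: "If the only post-baseline assessment is Stable Disease and it occurred prior to 6 weeks from first dose"

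Protocol 12.1.1 has a version of the third, "No post-baseline endpoint data subsequent to at least 1 dose of study drug", without the word *evaluable*, and has no counterpart to the fourth. SAP 14 lists neither difference as a change from the protocol. On replacement, Protocol 8.2 says: "Subjects who do not have post-baseline endpoint data subsequent to at least 1 dose of study drug may be replaced".

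**PFS.** SAP 9.2 runs PFS from Cycle 1 Day 1. A death is an event if it falls "within 126 days (approximately 2 time intervals for tumor assessments) of either first administration of tipifarnib or the last tumor assessment". Clinical progression documented by the investigator also counts, and a subject may be censored at the date of first administration. On display: "The median DOR and PFS and corresponding pointwise 95% confidence interval will be displayed by cohort for the FAS population", with the per-protocol set and the subgroups named as well.

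**OS.** SAP 9.3 runs OS from first dose to death and names no analysis population.

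**All dosed subjects.** The ASaT set is assigned to safety only. No PFS or OS analysis on it is planned.

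**The concern.** The PFS and OS clocks start at first dose, but entry to the FAS is decided later, by whether the subject yields an evaluable assessment of the right kind. A dosed subject whose event comes before that point can be removed along with the event. The clause that ties a death to first administration matters mainly for subjects who have no post-baseline scan. A scan-based FAS removes those same subjects, so SAP 6 and SAP 9.2 pull against each other.

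At stake are the median PFS by cohort and subgroup and, if it is run on the FAS, the median OS. Kaplan-Meier can carry an unscanned subject as an event or as censored, so nothing technical requires dropping anyone who was dosed.

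**Working it through.** **1. The plan's own figures.** The documents give no median, event count or exclusion count for PFS or OS. Their only operating characteristics belong to the two-stage ORR design (stop at 1 or fewer of 11, success at 4 or more of 18). Exact binomial sums reproduce them: one-sided alpha 0.0875 (stated 0.087), power 0.8001 (80%), early termination 0.6974 and 0.1130 (0.697 and 0.113). They do not bear on this point.

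**2. Whom the fourth exclusion reaches.** The first scheduled scan is Cycle 2 Day 22 ± 5 days (Protocol Table 1). That is study day 28 + 22 = 50, window 45 to 55. Six weeks is day 42, so a scheduled scan falls after the cut-off. Earlier scans are still possible: at the investigator's judgment (Protocol 8.1), or at End of Treatment about 30 days after the last dose (Protocol 11.6). A subject whose last dose is on day 7 could be scanned near day 7 + 30 = 37.

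Example: stable disease on day 35, no later scan, death on day 63. The death is 63 days after first dose and 28 days after the scan, both within 126. SAP 9.2 counts it as a PFS event and SAP 9.3 as an OS event. The fourth exclusion removes the subject.

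**3. Whom the third exclusion reaches.** The key term is undefined.

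| Dosed subject | SAP 9.2 | FAS, if endpoint data means a tumor assessment | FAS, if death or clinical progression also counts |
|---|---|---|---|
| Dies within 126 days of first dose, no evaluable scan | event | out | in |
| Clinical progression, no evaluable scan | event | out | in |
| Radiographic progression, however early | event | in | in |
| No scan, no event | censored at first dose | out | out |

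Only the first two rows can lose events. Removing the last row does not raise the curve.

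**4. Direction and size.** Let f be the share of dosed subjects dropped with early events. Once those events have passed,

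S_FAS(t) = S_dosed(t) / (1 − f),

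which is higher than S_dosed(t) whenever f > 0. The FAS median is the time at which S_dosed = 0.5 × (1 − f). For exponential times with median m, S_dosed(t) = 2^(−t/m), so

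FAS median / m = 1 + log2(1 / (1 − f)).

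| f (assumed) | ratio | FAS median if m = 4 months (assumed) |
|---|---|---|
| 0% | 1.000 | 4.0 |
| 5% | 1.074 | 4.3 |
| 10% | 1.152 | 4.6 |
| 15% | 1.234 | 4.9 |
| 20% | 1.322 | 5.3 |

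**5. In subjects.** With N subjects in the FAS and k dropped early events on top of them, the ratio is 1 + log2((N + k)/N).

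| N | k = 1 | k = 2 | k = 4 |
|---|---|---|---|
| 18 (Cohort 1) | 1.078 | 1.152 | 1.290 |
| 20 (Cohort 3) | 1.070 | 1.138 | 1.263 |
| 30 (HNSCC) | 1.047 | 1.093 | 1.181 |

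**6. Simulation check.** With an assumed true median of 3 months, dropping a random quarter or half of the events before day 50 removes 7.9% or 15.8% of subjects. The FAS median becomes 3.35 or 3.74 months. The formula gives 3.36 and 3.74.

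**The case against.** The strongest reply concerns the third exclusion. It speaks of endpoint data, not scans. Death and clinical progression are PFS endpoints in SAP 9.2, the option to censor at first administration presupposes unscanned subjects in the set, and SAP 7.6 keeps event-free dropouts as censored. On that reading the third exclusion loses no event. The reading is possible. Against it, SAP 3.1 defines the primary endpoint as RECIST response assessments, and the SAP added the word *evaluable*. The text does not decide, and two programmers could build different sets.

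Other replies stand in part:

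- **Reach.** The fourth exclusion needs an off-schedule or End of Treatment scan and no later one, so it will catch few subjects.
- **Size.** With a 4-month median, 1 − 2^(−1.64/4), or about 25%, of subjects have any event by day 50. A loss of f = 20% would need about four in five of those to lack an evaluable scan. ECOG 0 or 1 at entry and the End of Treatment imaging rules work against that.
- **Traceability.** SAP 9.2 promises per-subject PFS with censoring status and population membership, so dropped subjects can be found. No curve that includes them is planned.

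Three stronger inferences are tempting, and the documents do not support them:

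- **All early progressors are lost.** Radiographic progression keeps a subject in the FAS at any time.
- **The P value against prior therapy is biased toward tipifarnib.** That comparison is optional and names no population. SAP 8.3 draws the prior-therapy curves on the FAS too, so a dropped subject leaves both curves. The net effect depends on those subjects' earlier PFS and has not been computed.
- **The FAS was changed after the data were seen.** SAP version 4.0 (5 January 2021) cites data cuts of 10 April and 30 September 2020, but the documents do not show when the extra wording entered.

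**Conclusion.** The point holds in a limited form. Following the SAP as written can remove early PFS events that SAP 9.2 counts. This is certain for a subject with an early stable-disease scan who then dies within the 126-day limit with no later scan. For subjects who die or progress clinically without an evaluable scan, it depends on how an undefined term is read. Median PFS may therefore be inflated, by about 7% if 5% of dosed subjects are lost this way and about 15% if 10% are. These figures assume exponential times and that every dropped subject had an early event. The documents do not give the share, and it may be zero, so a flat statement that the medians are inflated would go too far.

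The same applies to OS only if it is run on the FAS. That is inferred from the general sentence in SAP 6. SAP 9.3 does not say so, although it does name populations for its waterfall and spider plots.

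PFS is exploratory and OS is an added analysis. Neither enters the primary ORR decision rule, which this point leaves untouched. The change is worth making but is not critical.

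**What to change.** - In SAP 9.2 and 9.3, make all dosed subjects (ASaT), by cohort and subgroup, the analysis set for PFS and OS.
- Handle unscanned subjects with the event and censoring rules that SAP 9.2 already ties to first administration. An unscanned subject with no event is then censored at first dose and does not move the curve.
- Keep DOR on responders.
- Show the FAS version of PFS and OS as supportive, and define in SAP 6 what counts as evaluable post-baseline endpoint data so that this version can be reproduced.
- List the added word *evaluable* and the early stable-disease exclusion in SAP 14 as changes from Protocol 12.1.1.

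The cost is SAP wording, one population flag and possibly slightly less favourable medians. No new data are needed.
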